TITLE: Evaluation of Abdominal Wall Block with Liposomal Bupivacaine for Post-Operative Analgesia in Donor Nephrectomy

NCT#: NCT03294109

DATE: May 20, 2020

Study Title:

“Evaluation of Abdominal Wall Block with Liposomal Bupivacaine for Post-Operative Analgesia in Donor Nephrectomy”

List of Abbreviations:

TAP block: Transverse abdominis plane block

TQL block: Transmuscular quadratus lumborum block

LA: Local Anesthetic

Principal Investigator, Research Team, and Study Site:

Principal investigators: [name] MD, [name] MD

Co-Investigators: [name] MD, [name] MD, [name] MD, [name] MD, [name], [name], [name]

Research team and contact information:

UCLA Department of Anesthesiology
and Perioperative Medicine

Ronald Reagan UCLA Medical Center

[name]

[name]

[contact]

University of California, Los Angeles

Department of Urology

David Geffen School of Medicine at UCLA

[name]

[name]

[name]

[contact]

Study site: UCLA Medical Center, Ronald Reagan Hospital

Background and study population

The study population will include patients greater than 18 years of age undergoing laparoscopic donor nephrectomy surgery.

Study Design

Randomized blinded controlled clinical trial

Sample Size

50 each arm. 100 total.

Study Duration

18-24 months.

Primary Objective

To determine the degree of pain control in patients receiving a long acting TQL block in addition to a short half-life TAP block compared to TAP block alone (i.e., the current standard of care) after laparoscopic donor nephrectomy. This outcome will be measured using pain scores on a numeric scale obtained during standard inpatient care as well as via the APS-POQR and PROMIS-29, two standard, validated questionnaires.

Secondary Objectives

- To determine patient satisfaction as measured by a satisfaction item at post-operative days 1 and 90.
- To measure changes in quality of life via the PROMIS-29, bowel function via the Bowel Habits Questionnaire (BHQ), male (International Index of Sexual Function; IISF) and female sexual function (Female Sexual Function Index; FSFI) across time and in the study group (patients receiving liposomal bupivacaine TQL block in addition to TAP block) as compared to our conventional post-operative pain management. See attached questionnaire schedule for timing of these items.

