- To determine if patient-reported nausea and vomiting at post-operative days 1, 3, 5, 10, and 30 is significantly decreased in patients in the study group.
- To measure the rate of block-related complications in the study group. Potential complications include local anesthetic toxicity, intravascular injection, persistent weakness or paresthesia, nerve injury, voiding dysfunction, persistent numbness, altered sexual function, bleeding/hematoma, hypotension, infection at the injection site, or other complaints related to the block.
- To determine if narcotic requirements postoperatively are lower in the study group. To determine total anesthetic and operative time, as well as costs.

Background and Significance:

Living kidney donors are carefully screened prior to recommending kidney donation. They are informed of the risks of surgery and the option of changing their mind until the day of kidney donation. All of the patients have an abdominal and pelvic CT scan to evaluate the renal anatomy and to screen for abnormalities. Our goal is to make the operation as minimally invasive as possible and to facilitate the return to normal function as quickly as possible. Currently, most patients need narcotics to control the pain after surgery. These medications can have significant side effects including nausea and constipation, which can delay recovery from the operation.

Since the first successful living donor kidney transplant between identical twins, the special nature of this operation and the anesthetic management has been debated (1). Extensive efforts have been made to improve the safety and reduce the morbidity of kidney donation. At UCLA, laparoscopic kidney donation was introduced in 1999, and is now the standard of care for approximately 150 of these operations annually. Ketorolac analgesia was added to reduce pain in 2002 and the procedure has continued to evolve to promote return to normal function as soon as possible (2). The median length of stay for these patients is currently 1.4 days.

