Liposomal bupivacaine is a novel local anesthetic designed for prolonged pain relief, up to 72 hours. Despite its long-acting analgesic potential, liposomal bupivacaine is significantly more expensive than other local anesthetic alternatives. The primary aim of this investigation is to examine whether or not liposomal bupivacaine provides superior pain relief, clinically significant

opioid-sparing effects, and improved patient satisfaction versus a control group with our current local anesthetic to justify its cost.

Objectives:

The primary objective of the study will be to determine the degree of improvement in pain control seen in patients receiving a TQL block in addition to our conventional method of TAP block compared to TAP block alone and intravenous/PO opioids based management. Both groups will have injection of 20 cc 0.25% bupivacaine in the transverse abdominus plane and subcutaneous infiltration of 10 cc around incisions. This is already our standard of care protocol. In addition to this standard care, the study group will receive a TQL block of 20 cc of liposomal bupivacaine mixed with 10 cc of normal saline will be under ultrasound guidance following induction of general anesthesia.

Both groups will have the same bowel preparation, ERAS fluid management, access to antiemetic, opioids, acetaminophen, and NSAIDs on a PRN basis. Assessments of pain scores will utilize the visual analog scale (VAS) evaluated by nursing staff when obtained with the vital signs per PACU and floor nursing protocol. Information regarding use of opioids after discharge will be collected with a pain diary and electronic surveys at least till 90 days. If a patient does not complete their 90 day survey the study team will contact them again to attempt an exit survey.

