Secondary objectives include patient satisfaction scores obtained with a validated satisfaction survey administered to each patient prior to discharge; nausea and vomiting requiring medical intervention; block-related complications noted in the immediate perioperative period or post-operative period; and total opiate requirement during the hospital stay and for 90 days after surgery. We will also monitor the return of bowel function, sexual function and general health using standardized quality of life instruments. Sexual function following kidney donation has not been closely evaluated; yet many patients ask about the potential impact of surgery on this bodily function that is important to a normal quality of life. Each patient will complete the validated survey instruments prior to and after kidney donation. Patients are not required to answer any questions. We will evaluate attitudes toward living kidney donation in relationship to pain control.

Study design/methodology:

This is a randomized, single-blinded controlled trial in patients greater than 18 years of age who have agreed to proceed with laparoscopic donor nephrectomy. Patients meeting these criteria will be offered participation in the study. They will be advised of the risks and potential benefits of the study. They will be advised of the request to answer surveys and have information regarding their care collected for research. They will be advised that participation requires the ability to answer questions using electronic communications. Participation is optional and standard anesthesia and pain control will be provided to all patients. Patients have the option to withdraw

from the study at any time and are not required to answer any of the survey questions. Enrolled patients will not know which treatment is provided.

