Those patients who agree to participate and provide written consent will be enrolled into the study and instructed in the electronic completion of study questionnaires using the Urology Patient Data Waystation (UPDW). Unique, personalized log-in information will be sent to the patient either by email or using the secure MyChart messaging system, based on patient preference, to access UPDW for each time point. Initial questionnaires at enrollment will collect baseline quality of life, bowel and sexual function, and demographic data. When the surgery date has been determined, patients will receive a message to complete a second set of baseline survey questionnaires using the same system if their surgery date is more than 6 months past the date of completion of their initial baseline survey. Those participants who completed their initial baseline within 6 months of their surgery date will only complete one baseline survey.

When surgery is scheduled, each enrolled patient will be randomized (alternating, blocked randomization) to either the study group to receive liposomal bupivacaine TQL block in addition to standard of care post-operative pain management or to the control group to receive our current standard of care. Randomization will maintain equal numbers of participants in each group by sex due to the increased risk of post anesthesia nausea in females.

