The following study variables will be collected postoperatively following arrival in the post-anesthesia care unit: Current and maximum intensity pain scores will be documented by nurses in the electronic medical record (EMR). Total opiate dose consumed every 24 hours will be collected from EMR and electronic survey after discharge. Patient satisfaction will be evaluated using the Revised American Pain Society Patient Outcome Questionnaire (APS-POQ-R) provided on post-operative day 1 by a research assistant or study coordinator. The incidence of nausea or vomiting will be extracted from nursing notes and queried via electronic surveys. Post-discharge, which is typically 1-2 days following surgery, patients will be sent surveys delivered by the UPDW database server 3, 5, 10, 30, and 90 days post-surgery. If patients do not respond 90 days post-surgery study team will contact patients to attempt to have the exit survey completed.

Complications will be documented in the EMR by the anesthesia pain service, urology service, and nurses who will monitor these patients while admitted. Urology and study staff will follow the patients following discharge, including a post-operative office follow-up approximately 1 week post-surgery, as is standard of care

Study Population:

Patients at least 18 years of age undergoing laparoscopic donor nephrectomy. Pregnant patients will be excluded. Patients with local infection at the potential block site or any contraindication to kidney donation, local, or general anesthesia will be excluded.

Study Duration/Study Timeline:

We anticipate a high level of enrollment since most patients have previously consented to having a block placed and pain minimization is generally a high priority. Given the current volume of donor nephrectomies we expect enrollment to be complete within one year. The duration of the study will depend on the timing from consent for surgery until the operation is scheduled. In most cases this occurs within 2-3 months. The study data collections will conclude 90 days after surgery unless the patient was not able to complete the survey. Additional attempt to contact the patient after 90 days post-surgery may be enacted to have the patient(s) complete an exit survey. See the attached study time line in Appendix A.

Statistical Analysis Plan:

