If returning to the clinic for an additional consent visit would be too burdensome for the patient – many eligible patients drive or fly several hours to attend appointments at UCLA – the study coordinator will arrange for the patient to complete consent by mail. To do so, the study coordinator will give the patient two copies of the consent form, the HIPAA form, the patient bill of rights, and a pre-paid envelope for returning signed documents. The envelope will be addressed to [name] and delivered to his locked office. The study coordinator will follow up with the patient within approximately 2 weeks to determine whether the patient has made a decision on whether to participate and again probe for further questions, which will be answered by the study coordinator or forwarded to a study surgeon depending on the content. Once the patient has made a decision, the study coordinator will schedule an appointment for the patient to speak with a study surgeon to confirm all questions have been answered and to complete the consent process. The patient may then place the signed consent and HIPAA forms in the pre-paid envelope to mail to the study team. Once the forms are received, the study coordinator will enroll the patient and send the baseline survey as usual. Regardless of methodology, the consent

process will be documented, including date and time of consent, via paper forms which will be stored with the consent form and signed by the physician obtaining consent.

Patients will be recruited until our goal sample size of 50 patients in each arm of the study is achieved. At that time statistical analysis will be performed. Any major complications will be reviewed to determine if the study should be continued.

Privacy and confidentiality:

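### The efficacy analysis is timed to the end of recruitment, although outcomes run to day 90 after surgery; the final analysis should be tied to the end of follow-up (minor)

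*Combined protocol and SAP*

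**What the plan says.** The timing rule stands at the end of the recruitment text in Informed Consent Process. Recruitment continues until the target of 50 patients "in each arm of the study is achieved. At that time statistical analysis will be performed". The following sentence adds that major complications will be reviewed to decide whether the study goes on.

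Outcomes extend well beyond that moment:

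- Secondary Objectives (opening summary): "To determine patient satisfaction as measured by a satisfaction item at post-operative days 1 and 90".
- Secondary Objectives, on nausea: "patient-reported nausea and vomiting at post-operative days 1, 3, 5, 10, and 30".
- Objectives, post-discharge opioids: "Information regarding use of opioids after discharge will be collected with a pain diary and electronic surveys at least till 90 days".
- Objectives, secondary: "total opiate requirement during the hospital stay and for 90 days after surgery".
- Study design/methodology and Study Duration/Study Timeline: surveys go out up to day 90, with further contact after day 90 for an exit survey if a patient has not responded.

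The Statistical Analysis Plan section names t-tests for pain, nausea, 24-hour opiate consumption and satisfaction. It gives no data cut-off or condition on follow-up. Data Safety Monitoring separately plans intermittent analysis of adverse outcomes for at least 90 days after surgery. On accrual, Study Duration/Study Timeline says "we expect enrollment to be complete within one year"; the opening summary gives a study duration of 18-24 months.

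**The concern.** The end of recruitment is the only time that the visible text gives for the efficacy analysis. At that moment the most recently recruited patients cannot have reached day 30 or day 90, whatever the accrual pattern; only their number depends on assumptions. If the sentence were followed as the rule for the final analysis, these patients would be missing from the later satisfaction, nausea and opioid comparisons because they were not yet due, not because they dropped out.

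The text also leaves open whether this analysis is final or interim. If it is final, late data are left out. If it is interim, nothing is lost, but the final analysis then has no stated time. The sentence needs clarifying either way.

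**Working it through.** **Inputs**

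- N = 100 patients, 50 per arm (Sample Size).
- Accrual A = 365 days (Study Duration/Study Timeline). Uniform accrual is an assumption.
- Outcome day d = 90 for satisfaction and opioids, d = 30 for the last nausea assessment.
- Lag L = days from the event that counts a patient as recruited to surgery. The plan does not define that event. Base case: counted on the day of surgery, L = 0 (assumption).
- Every counted patient is operated on and responds when due (assumption).

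**The plan's own figure.** The plan gives no count of patients lacking late data. Its sample-size basis is Table 1: means 7 and 5, SD 3, 80% power, 37 per group. A two-sample t-test at two-sided 0.05 (assumed, as no alpha is stated) reproduces 37 and the other eight rows. The plan goes from 37 to 50 per arm to allow for non-completion, without stating a rate.

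**Patients without day-d data when the last patient is counted** = N × (d + L) / A.

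1. Day 90, L = 0: 100 × 90 / 365 = 24.7, or about 12.3 per arm, leaving 50 − 12.3 = 37.7 per arm. A direct count of 100 evenly spaced patients gives 25. In 5,000 simulations with uniformly random recruitment dates the mean is 25.7, with a 95% range of 18 to 34.

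2. Day 30, L = 0: 100 × 30 / 365 = 8.2.

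3. Sensitivity to accrual time (L = 0, day 90), with the standard error relative to all 100 patients = √(100 / number with data):

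| Accrual | Days | Without day-90 data | Standard-error ratio |
|---|---|---|---|
| 10 months | 304.2 | 29.6 | √(100/70.4) = 1.19 |
| 12 months | 365 | 24.7 | √(100/75.3) = 1.15 |
| 15 months | 456.25 | 19.7 | √(100/80.3) = 1.12 |
| 18 months | 547.5 | 16.4 | √(100/83.6) = 1.09 |

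4. Counting at randomization. Study design/methodology randomizes when surgery is scheduled, so before the operation, and the lag is not given. With 12-month accrual each assumed 30 days of lag adds 100 × 30 / 365 = 8.2 patients; L = 30 gives 100 × 120 / 365 = 32.9. The added patients would not yet have been operated on, so they would lack inpatient data too.

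5. Earliest analysis after full follow-up (12-month accrual, L = 0): 12 + (90/365) × 12 = 15.0 months.

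**The case against.** The strongest reply is that this is loose drafting. The sentence sits in the recruitment text, not in the Statistical Analysis Plan section, and may mean only that analysis follows recruitment. The protocol commits to day-90 surveys and to contact afterwards. A duration of 18-24 months against one year of enrollment leaves at least six months after accrual. Appendix A and the questionnaire schedule are cited but are not in the text available, and either could fix the timing. Patients not yet due are delayed, not lost. Most of this stands, and it is why the point is minor. But a study duration does not set an analysis time, and the sentence as written does.

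A reader might infer more than the documents support:

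- *That no other analysis is timed.* Data Safety Monitoring plans intermittent safety analysis. The sentence on reviewing complications fits that review and need not mean an interim efficacy look.
- *That 25 is a minimum.* It holds for uniform 12-month accrual. Front-loaded or slower accrual gives fewer, and chance alone gives 18 to 34.
- *That the 2-3 months in Study Duration/Study Timeline is the lag from randomization to surgery.* That interval starts at consent for surgery, whereas randomization comes when surgery is scheduled.
- *That the trial would be underpowered because 37.7 per arm uses nearly all the allowance above 37.* Table 1 concerns pain scores. No power calculation is given for a day-90 outcome, so the comparison shows scale only.

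**Conclusion.** The conflict between the stated analysis time and the day-90 outcomes is real, but minor and probably unintended. Taken literally as the final analysis, it leaves about 25 of 100 patients without day-90 data and about 8 without day-30 data, under uniform 12-month accrual with patients counted at surgery. The day-90 figure falls to about 20 at 15 months and 16 at 18 months, and rises by an unknown amount if patients are counted at randomization.

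The cost is precision: a day-90 standard error about 15% larger in the 12-month case. No bias between arms is claimed. Inpatient pain and 24-hour opioid use are little affected if patients are counted at surgery. The primary objective also draws on questionnaires whose full schedule is not in the text, so the effect on those cannot be judged. Appendix A may already resolve the timing, in which case the recruitment text should be made to agree with it.

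**What to change.** Replace the sentence on analysis timing with: *Recruitment then stops; the final analysis is performed after every randomized patient has completed the day-90 assessment or exit contact, passed its window, or been recorded as withdrawn or not operated on.*

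The last clause is needed because randomization precedes surgery and, according to Background and Significance, donors keep "the option of changing their mind until the day of kidney donation". For the window to close, the plan should also give a last day for the exit contact; the visible text gives none. State whether any earlier efficacy analysis is planned, and align the wording with Appendix A.

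The cost is a few sentences and a later start: at least about 3 months after the last patient is counted. With 12-month accrual counted at surgery that is about month 15, within the stated 18-24 months. Counting at randomization adds the lag to surgery, and exit contact adds whatever window is chosen.
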